### **3.2 Study population, exposures, outcomes and covariates**

#### **3.2.1 Study populations/subgroups**

##### *Study population for main analysis (primary objective and secondary objective #1)*

- Pregnant women received prenatal care at KPSC
- Exposed cohort: vaccinated with Boostrix on the 1st day of the 27th week of pregnancy or later during the pregnancy and were not vaccinated with any other Tdap vaccine at any other time during the pregnancy or
- Unexposed cohort: pregnant at least one day during the approximate estimated period between 1/1/2012-12/31/2013 and did not receive any Tdap vaccine during the pregnancy
- Continuous membership (allowing up to a 31-day gap) between the 1st day of the 27th week of pregnancy and the index (vaccination) date

The unexposed cohort will be 1:1 matched to the exposed cohort on age at pregnancy start ( $\pm 1$  year), race/ethnicity (White, Black, Hispanic, Asian, and Other), and multiple gestation (yes/no). Every unexposed woman will be assigned an index date that is determined by the number of days from pregnancy start to the Boostrix vaccination date of her matched exposed woman. The same number of days calculated in the exposed woman will be added to the pregnancy start of the unexposed woman to determine her index date.

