### 3.2.4 Covariates

Covariates (Table 2) to be collected and explored include medical conditions indicative of a high-risk pregnancy and other relevant baseline characteristics. The algorithms for identification of high-risk medical conditions are described in the DMP.

Table 2. List of covariates (all covariates will be treated as categorical in the analyses)

High-risk medical condition
Thyroiditis (present/absent)
Diabetes (present/absent)
Other autoimmune diseases (present/absent)
Renal diseases(present/absent)
Cardiac diseases (present/absent)
Pre-pregnancy obesity (BMI>40: yes/no/missing)
Pre-existing hypertension (present/absent)
Rhesus sensitization (present/absent)
HIV infection (present/absent)
Syphilis infection (present/absent)
Cervical incompetence (present/absent)
Lifestyle factors
Smoking status from pregnancy start to index date (Yes/No)
Alcohol use from pregnancy start to index date (Yes/No)

Enrollment
Length of membership prior to 27 weeks gestation (but after pregnancy start) – having continuous membership from pregnancy start to index date (Yes/No)
Medicaid insurance (public health insurance: Indicator of low-income status) – any Medicaid enrollment from pregnancy start to index date (Yes/No)
Utilization
Health care utilization (receipt of medical care) from pregnancy start to index date
Any hospitalization or ED visit (Yes/No)
Number of outpatient visits (0-4/5-12/ $\geq 13$ )
Maternal Data
Number of previous pregnancies (0/1/ $\geq 2$ /Missing)
History of pregnancy loss (Yes/No)
Season of pregnancy start (September-March/April-August)
Vaccine
Receipt of other vaccines during pregnancy, e.g., influenza vaccine (Yes/No)
Receipt of vaccines containing diphtheria, tetanus toxoid or pertussis antigens within one year before pregnancy (Yes/No)
Matching variables
Race/Ethnicity (White/Black/Hispanic/Asian/Other)
Multiple gestation (Yes/No)
Age at pregnancy start (years)

Smoking status will be defined as current smoker or not. If patients reported they smoked any time from pregnancy start to index date, then they will be current smokers. Alcohol use will be defined in a similar fashion.

Length of membership prior to 27 weeks gestation (but after pregnancy start) will be defined as a dichotomous variable of having continuous membership (allowing up to a 31-day gap) from pregnancy start to index date.

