Health care utilization will be defined as any hospitalization or emergency department (ED) visit, and number of outpatient visits (0-4, 5-12,  $\geq 13$ ) from pregnancy start to index date.

Receipt of other vaccines during pregnancy will be defined as any receipt of other vaccines from pregnancy start to index date.

The covariates included in adjusted analyses will be determined by scientific relevance, association with exposure and outcome, and data availability. Specifically, we will select covariates by following these steps:

1. The distribution of covariates will be reviewed. Those covariates in the same category with rare events will likely be combined as a single covariate. For example, we might consider grouping all chronic conditions into a single covariate.
2. The data availability will be checked. If a covariate contains a large proportion that is missing, and the proportion missing is differential by exposure, then the covariate may not be included.
3. Association of covariates with exposure will be assessed. We will use standardized difference to assess the balance of covariates between exposed and unexposed cohorts. Unlike p-values, for which magnitude is highly related to sample size, standardized difference is a unified approach to quantifying the magnitude of difference between groups regardless of sample size, where an absolute value less than 0.1 is considered a negligible difference (3). We will use a SAS macro %stddiff developed by PPD and PPD (4) to calculate the standardized differences for continuous and categorical variables. Potential confounders will be determined by absolute standardized difference (ASD)  $>0.1$ .
4. Association of potential confounders (identified from step 3) with each primary endpoint will be further assessed using a change-in-estimate approach (5). Diabetes, pre-existing hypertension (except for the analysis of the preeclampsia and/or eclampsia endpoint), Medicaid insurance, and health care utilization, which are considered as the most representative prognosis factors, will be kept in the adjusted model regardless of their association with exposure and primary endpoints. For a specific endpoint, the exposure coefficient estimate from a model adjusted for the 4 above covariates will be compared with the estimate from a model adjusted for one more covariate at a time. Covariates which result in a 10% change in the exposure coefficient estimate will be selected for final adjusted analysis.

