### 3.3 Sample Size and Power Considerations

The power computation for the primary objective was performed using PASS non-inferiority of two independent proportions using Miettinen and Nurminen method. Although the power is not based on the Poisson regression model, it is expected to reflect the power on the planned analysis since inference on proportion and incidence rate provide similar results when incidence rates are low.

The following table (Table 3) shows the power to rule out a two-fold increase considering an assumed possible design bias leading to a 1.25 relative risk increase.

To be able to make independent conclusions for each of the four primary endpoints while controlling the type I error below 2.5%, a Bonferroni adjustment will be used, i.e., each primary endpoint will be evaluated using a one-sided 0.625% (2.5% type I error / 4 primary endpoints) nominal type I error. More specifically, the upper limit of the two-sided 98.75% confidence interval (CI) will be used to make conclusions.

Considering that the four primary endpoints are expected to have an incidence rate above 1%, the power to conclude that maternal immunization is non-inferior for any primary endpoint is at least 95% and the power to conclude that maternal immunization is non-inferior for all 4 primary endpoints is at least 80% (100% - 4\*beta).

Table 3. Power to rule out a two-fold increase with 15,000 pregnant women in each cohort

Incidence rate in unvaccinated cohort	One-sided type I nominal error	True relative risk	Power	Beta
1%	0.625%	1.25	95.7%	4.3%

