##### 4.2 Analyses of primary endpoints

We will calculate crude incidence and 95% CI for each primary endpoint for the exposed and unexposed cohorts. Unadjusted and adjusted RR with two-sided 98.75% CI will be estimated comparing the exposed cohort to the unexposed cohort, accounting for multiple comparisons.

Analysis of primary endpoints will be used to evaluate the safety of Boostrix vaccination and concluded to be non-inferior if the upper limit of the 98.75% CI for the adjusted relative risk is below 2.

Analyses of preeclampsia and/or eclampsia and intra-uterine infection will be performed on all pregnant women eligible for main analysis. For events identified any time after the index date (e.g., preeclampsia and/or eclampsia and intra-uterine infection), the incidence will consist of the total number of women with the condition in the numerator and the total person time in the denominator. The person-year for a pregnant woman will be the time from the index date to the date of each adverse event, end of the pregnancy, or disenrollment, whichever comes first. The unadjusted and adjusted relative risk with 98.75% CI will be estimated by Poisson regression models accounting for the follow-up time without and with adjustment for potential confounders. If the outcome is common (i.e., incidence > 2%), a Poisson regression model with a robust error variance will be used to estimate the relative risk (6). The robust Poisson regression will be performed using the SAS Proc GENMOD procedure with the REPEATED statement subject= Patient\_ID.

Analysis of SGA will be performed on live singleton infants born in KPSC hospitals, while analysis of preterm delivery will be performed on pregnant women with live births, and with an index date prior to 37 weeks gestation. For events identified at delivery (e.g., SGA and preterm delivery), the incidence will consist of the total number of women or infants with the condition in the numerator and the number of women or infants for whom the condition can be assessed in the denominator. The unadjusted and adjusted relative risk with 98.75% CI will be estimated by Poisson regression models with robust error variances without and with adjustment for potential confounders. The planned methods of analysis by primary endpoint are outlined in Table 4. See Appendix A, Table Shell 4 for details.

Table 4. Analytic population and statistical methods by primary endpoint

Primary endpoints	Analytic population	Statistical Methods

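### Utilization counted up to the index date is forced into the primary models without gestational age at index, so the adjusted preeclampsia and infection RRs can be biased if visit frequency differs between eras

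*SAP*

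**What the plan says.** All references are to SAP Final 2.0 unless stated.

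- **Index date (3.2.1).** "Every unexposed woman will be assigned an index date that is determined by the number of days from pregnancy start" to vaccination in her matched exposed partner. Gestational age at index is therefore the same within each pair.
- **Covariates (3.2.4, Table 2).** Gestational age at index is not listed, either as a covariate or under the matching variables (race/ethnicity, multiple gestation, age). Table Shell 2 describes it in three bands (27-30, 31-36, 37 or more weeks) with no p-value. Section 4.2 puts the matching variables into the SGA and preterm delivery models only.
- **Utilization (3.2.4, Table 2).** "Health care utilization (receipt of medical care) from pregnancy start to index date" comprises any hospitalization or ED visit, and outpatient visits in the classes 0-4, 5-12 and 13 or more.
- **Selection (3.2.4, steps 3-5).** A covariate must show an absolute standardized difference (ASD) above 0.1 to become a candidate, and step 4 tests only those candidates. Four are exempt, among them "Medicaid insurance, and health care utilization, which are considered as the most representative prognosis factors, will be kept in the adjusted model regardless" of association. For secondary endpoints, step 5 enters whatever passed the ASD screen.
- **Model (4.2).** For preeclampsia/eclampsia and intra-uterine infection the RR is "estimated by Poisson regression models accounting for the follow-up time without and with adjustment for potential confounders". Person-time runs from index to event, end of pregnancy or disenrollment, with no term for gestational time. The adjusted RR decides non-inferiority.

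**The concern.** Index-date assignment balances a strong determinant of the event rate per person-year. A woman indexed at 37 weeks contributes only a short stretch of follow-up, all near term. A woman indexed at 28 weeks contributes many low-risk weeks. The crude RR benefits from that balance.

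The forced utilization terms partly stand in for index age, because a longer window collects more visits. Suppose women in 2018-2019 made more visits at a given gestational age than women in 2012-2013. An exposed woman then reaches a given visit class earlier in pregnancy than an unexposed woman does. Within that class the exposed have the lower index age and hence the lower rate, and the adjusted RR falls below its true value. With fewer visits in the exposed, the RR rises.

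The SAP's own procedure cannot repair this. The variable that would do so is balanced overall, fails the ASD screen and never reaches step 4. At stake is bias in the two reported adjusted RRs that carry a person-time offset. SGA and preterm delivery use no person-time, and no shift was calculated for them.

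**Working it through.** **1. The plan's own figure.** Inputs from SAP 3.3: "each primary endpoint will be evaluated using a one-sided 0.625% (2.5% type I error / 4 primary endpoints) nominal type I error" (z = 2.4977); n = 15,000 per cohort; unexposed incidence 1%; true RR 1.25; margin 2. In the score test of p1 = 2·p0, the estimates constrained to the null are 0.014987 and 0.007494.

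- Null SE of (p1 − 2·p0) = √{[0.014987(1 − 0.014987) + 4·0.007494(1 − 0.007494)]/15,000} = 0.0017227
- SE under the alternative = √{[0.0125·0.9875 + 4·0.01·0.99]/15,000} = 0.0018609
- Power = Φ[(0.0075 − 2.4977·0.0017227)/0.0018609] = Φ(1.718) = 95.7%, as stated.

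**2. How much index age varies.** In Protocol Table 4, 3,500 + 943 = 4,443 of the 19,554 women vaccinated at 27 weeks or later (23%) were vaccinated at 33 weeks or later.

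**3. How much the rate varies with index age.** Take 5.5% infection (the unvaccinated chorioamnionitis figure in Protocol 1.1) and assume it occurs at delivery. The rate is then 0.055 divided by mean follow-up in years. Simulated index ages gave about 0.27 per person-year for women indexed before 30 weeks (0.055/0.27 = 0.20 years, about 10.6 weeks) and about 1.8 from 37 weeks (0.055/1.8 = 0.031 years, about 1.6 weeks). Table 4 does not split the 27-32-week band, so the first figure assumes a spread within it.

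**4. Mechanism.** In visit class k, the rate in cohort j is Σg wjk(g)·λ(g). Here λ(g) is the rate at index age g and wjk(g) is the share of that class's person-time at g. With true RR 1, the class-specific ratio departs from 1 only if three things hold together:

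- visits rise with g;
- λ rises with g;
- visits at equal g differ between cohorts.

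**5. Size.** True RR set to 1, Table 4 index-age bands identical in both cohorts, Poisson model with person-time offset, exposure and the three visit classes. Not in the documents, and therefore assumed: the visit distribution, the visit difference, the preeclampsia hazard by week, and delivery centred near 39 weeks. The ranges below come from simulations with differing assumed inputs.

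| Visits in exposed vs unexposed | Infection RR | Preeclampsia RR |
|---|---|---|
| Equal | 1.00 | 1.00 |
| 15% more | about 0.97 | about 0.985-0.99 |
| 30% more | about 0.95 | about 0.97-0.98 |
| 15% fewer | about 1.03 | about 1.015-1.02 |

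Adding index week brought each RR back to its crude value.

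An expected-count calculation covered a wider set of assumptions: mean 7-12 visits at 28 weeks, rising 0.5-1 per week; Poisson or negative-binomial spread; hazard rising 12% or 25% per week. For visit ratios of 0.7-1.4 it gave 0.917-1.087 for preeclampsia and 0.853-1.172 for infection. A constant hazard gave 1.000 at every ratio. At ratio 1.25 the unadjusted RR was 1.000, and adding index age returned the adjusted RR to 1.000.

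**6. Effect on the decision.** The largest point RR that passes solves ln RR + 2.4977·√[(1 − p1)/(n·p1) + (1 − p0)/(n·p0)] = ln 2.

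- At p0 = 1% it is about 1.54.
- At p0 = 5.5% it is about 1.80: p1 = 0.099, SE = √(0.901/1,485 + 0.945/825) = 0.0419, and 0.588 + 0.105 = 0.693.
- Downward shift: at 5.5%, a factor of 0.953 changes a fail into a pass only if the unshifted estimate lies between 1.80 and 1.80/0.953 = 1.89.
- Upward shift: raising 1.25 by 2% or 5% (to 1.275 or 1.3125) reduces power at 1% incidence from 95.7% to about 94% or 91%. At 2% incidence power stays at or above 99.8%.

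**The case against.** The case for leaving the plan alone has real force.

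- **No evidence of a visit difference.** Neither document gives visit counts for either cohort. SAP 5.4 only names changed health-seeking behavior as a possibility. This stands: the bias is conditional.
- **The margin absorbs it.** The plan already powers "considering an assumed possible design bias leading to a 1.25 relative risk increase", and SAP 5.3 says the margin allows for incompletely adjusted bias. This stands for the primary decision. It does not make the reported RR unbiased.
- **Utilization may be a true confounder.** The calculations give visits no prognostic value of their own, so dropping utilization could do harm. This stands, and the fix keeps utilization.
- **The output would show it.** Crude and adjusted RRs appear side by side, and Table Shell 2 gives visits and index age by cohort. This stands only in part: a gap between crude and adjusted RR could equally be real confounding removed, and the tables cannot tell the two apart.
- **Rare endpoints cannot carry many index-week terms.** This stands. SAP 3.2.4 step 5 expects non-convergence, and adjusted analysis is dropped below 5 total events.

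A reader might infer that adjustment undoes the index-date matching. It does not: overall balance and the unadjusted RR are untouched. A reader might also infer that a constant event rate is itself a source of bias. With index age balanced it is not. An effect would need a shift in delivery timing between eras, which the documents do not report. With an assumed delivery 0.8 day earlier in the exposed, simulated preeclampsia RRs ranged from a negligible change to 0.967, depending on the assumed hazard.

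**Conclusion.** The omission is certain from the text. Gestational age at index is in no model and cannot enter through the screen, while utilization accumulated up to that date is forced into all primary models. The bias in the preeclampsia/eclampsia and intra-uterine infection RRs is conditional. It is zero if visits at equal gestational age do not differ between eras, or if the event rate does not depend on index age. Under assumed visit differences of 15-30% it is about 1-3% for preeclampsia and 3-5% for infection, in either direction. The wider assumptions reach about 9% and 17%.

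It would be tempting to read this as a fixed downward shift that favours non-inferiority, or as a threat to the primary conclusion. The documents support neither. They fix no sign, and a shift of this order changes the result only for an estimate already close to the passing limit. This is a low-cost improvement in freedom from bias.

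**What to change.** 1. **SAP 3.2.4 step 4 and 4.2.** Force gestational age at index, categorical or as a spline, into the adjusted models for preeclampsia/eclampsia and intra-uterine infection, whatever its ASD. Alternatively, count outpatient visits and hospital/ED use over a fixed window such as pregnancy start to the start of week 27.
2. **SAP 3.2.4 step 5 and 4.3.** For the secondary person-time endpoints, do the same only when utilization enters the model and event counts allow, using the coarse bands of Table Shell 2 (27-30, 31-36, 37 or more weeks). The case is worth covering: in one simulation a 15% visit difference gave an ASD of about 0.23, so utilization would enter, and the signal rule there (lower 95% limit above 1) has no margin to absorb bias.
3. **Optional sensitivity analyses.** Split person-time by gestational week, and report an infection RR per woman without the offset.

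The cost is a few extra parameters and no new data. The fixed-window option ignores care received between week 27 and a later index date.

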6.2. Statistical methods

6.2.1. Covariates

Baseline characteristics of pregnant women and information on other relevant covariates will be extracted through automated data. Data will be in the form of International Classification of Diseases, 9th or 10th Revision (ICD-9 or ICD-10) codes or structured data fields. While data on these characteristics will be collected, only the potential

confounders associated with the exposure or outcome will be considered in adjusted analyses and will be a subset of the covariates of interest. Identification of the potential confounders will be determined through bivariate analyses and by prior knowledge based on the literature (22).

Medical conditions indicative of a high-risk pregnancy to be considered as covariates include:

- thyroiditis,
- diabetes,
- other autoimmune diseases (mixed connective tissue disease such as systemic lupus erythematosus),
- renal and cardiac chronic diseases,
- obesity (pre-pregnancy BMI>40),
- pre-existing hypertension,
- Rhesus sensitization,
- HIV infection,
- syphilis infection,
- cervical incompetence.

Some additional covariates of interest to be collected and explored (if data are available) include:

- smoking status
- alcohol use
- length of membership prior to 27 weeks gestation (but after pregnancy start)
- health care utilization (receipt of medical care) prior to the index date (but after pregnancy start)
- number of previous pregnancies
- history of pregnancy loss
- receipt of other vaccines during pregnancy, e.g., influenza vaccine
- receipt of vaccines containing diphtheria, tetanus toxoid or pertussis containing antigens within one year before pregnancy
- season of pregnancy start
- Medicaid insurance (public health insurance: Indication of low income status)

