5. All potential confounders (identified from step 3) will be included in the analyses of secondary endpoints. If the outcome is rare and the adjusted model cannot converge, problematic covariates will be removed from the model. If total counts from the two groups (i.e., sum of events in the exposed and unexposed cohorts) is less than 5, then no adjusted analysis will be performed.

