##### 4.1 Description of study population

The size of the study population and subgroups for main analysis will be described, overall and by exposed and unexposed cohorts. See Appendix A, Table Shell 1 for details. The number and percentage of pregnant women with unknown pregnancy outcome, lost to follow up, and multiple gestation will also be reported.

Baseline characteristics will be described and compared between the exposed and unexposed cohorts. See Appendix A, Table Shell 2 for details. Bivariate analyses will be conducted for all covariates of interest. Continuous variables such as age in years will be summarized by mean, median, Q1, Q3, range, and standard deviation and compared using t-tests; categorical variables will be summarized by frequency and percentage and compared using chi-square tests or Fisher's exact test, as appropriate. Absolute standardized difference will be calculated to assess the balance of covariates. Potential confounders will be determined based on bivariate analyses and scientific relevance (see Section 3.2.4).

Birth outcomes captured among KPSC born infants (birth weight, length, head circumference, and Apgar scores) will be described for exposed and unexposed cohorts. See Appendix A, Table Shell 3 for details.

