### 4.3 Analyses of secondary endpoints

The analysis of secondary endpoints will be used for hypothesis generation/signal detection. We will calculate crude incidence and 95% CI for each secondary endpoint for the exposed and unexposed cohorts. Unadjusted and adjusted RR with two-sided 95% CI will be estimated comparing the exposed cohort to the unexposed cohort. At least one case in each cohort is required to perform unadjusted and adjusted analyses. If total counts from the two groups is less than 5, then no adjusted analysis will be performed. An elevated risk will be detected if the lower limit of the 95% CI for the adjusted relative risk is above 1. The planned methods of analysis by secondary endpoint are outlined in Table 5. See Appendix A, Table Shell 4 for details.

Table 5. Analytic population and statistical methods by secondary endpoint

Secondary endpoints	Analytic population	Statistical Methods
Transfusion during delivery hospitalization	Pregnant women with delivery hospitalization	Adjusted Poisson regression model
Poor fetal growth	All pregnant women eligible for main analysis	Adjusted Poisson regression model accounting for follow up time, with robust variance estimate
Stillbirth/fetal death*	Pregnant women with pregnancy outcome	Adjusted Poisson regression model
Neonatal death	KPSC live born infants	Adjusted Poisson regression model
Maternal death	All pregnant women eligible for main analysis	Adjusted Poisson regression model accounting for follow up time
Placental abruption	All pregnant women eligible for main analysis	Adjusted Poisson regression model accounting for follow up time
PPROM	All pregnant women, with index (vaccination) date prior to 37 weeks gestation	Adjusted Poisson regression model accounting for follow up time
Congenital anomalies (CA) by type	KPSC live born infants	Adjusted Poisson regression model, with robust variance estimate if outcome is common

\*Stillbirth/fetal death will be described with or without congenital anomalies separately, but will be analyzed as one outcome.

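### The prognostic factors forced into the primary models are not carried into the secondary models, where tests against RR = 1 are more sensitive to small residual confounding

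*SAP*

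**What the plan says.** The opening text of SAP 3.2.4 refers to scientific relevance, association with exposure and outcome, and data availability, and then gives numbered steps by which covariates will specifically be selected.

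- **Step 3** labels a covariate a potential confounder if its ASD between cohorts exceeds 0.1. A smaller difference is called negligible.
- **Step 4** (primary endpoints) names diabetes, pre-existing hypertension, Medicaid insurance and health care utilization as the leading prognostic factors. These "will be kept in the adjusted model regardless of their association with exposure and primary endpoints". Hypertension is exempted for preeclampsia/eclampsia, so three factors are forced there and four for the other three endpoints. The remaining step 3 covariates face a further filter: "Covariates which result in a 10% change in the exposure coefficient estimate will be selected for final adjusted analysis".
- **Step 5** (secondary endpoints): "All potential confounders (identified from step 3) will be included in the analyses of secondary endpoints". It names no forced factor and applies no change-in-estimate filter. Problematic covariates are removed if the model does not converge, and no adjusted model is fitted with fewer than 5 events in total.

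The secondary decision rule is in SAP 4.3: "An elevated risk will be detected if the lower limit of the 95% CI for the adjusted relative risk is above 1". The primary rule in SAP 4.2 compares the upper 98.75% limit with 2. Protocol 6.2.1 is wider than step 5, since there "confounders associated with the exposure or outcome will be considered in adjusted analyses".

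**The concern.** Read literally, a factor that the SAP itself regards as strongly prognostic is guaranteed a place in the primary models but enters a secondary model only if its ASD exceeds 0.1. At an ASD of 0.09, diabetes or hypertension would be absent from the models for poor fetal growth, placental abruption, PPROM, stillbirth and transfusion.

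The ASD measures imbalance only. Confounding depends on imbalance and on the strength of the link to the outcome, so a modest imbalance in a strong risk factor still biases the RR by a few percent. Against a margin of 2 that hardly matters; against a null of 1 it can move the rate of declared signals. The cohorts are several years apart, and SAP 5.4 acknowledges secular confounding and possible confounding by indication, so imbalance in these factors is plausible in either direction.

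**Working it through.** **The plan's own figure.** SAP 3.3 gives 95.7% power to rule out RR of 2 or more (1% control incidence, true RR 1.25, 15,000 per cohort, one-sided 0.625%). The Miettinen–Nurminen normal approximation gives 95.71%, so it reproduces. It concerns the primary endpoints only; the documents give no power or incidence figures for the secondary tests.

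**Inputs.** From the documents: 15,000 per cohort (SAP 3.3), the 0.1 ASD cut-off (SAP 3.2.4) and the 95% lower-limit rule (SAP 4.3). Assumed, because the documents give none: covariate prevalences, covariate–outcome RRs and secondary incidences of 0.1% to 3%.

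**Step 1: imbalance that passes under the cut-off.** ASD = |p1 − p0| / √[(p1q1 + p0q0)/2], with q = 1 − p.
- Hypertension 3.0% vs 4.8%: 0.018/0.1934 = 0.093.
- Diabetes 10% vs 13%: 0.030/0.3187 = 0.094. Medicaid is given the same prevalences.

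All would be left out under step 5.

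**Step 2: resulting bias.** Bias = [1 + p1(r − 1)] / [1 + p0(r − 1)], where p1 and p0 are the exposed and unexposed prevalences and r is the factor's outcome RR.
- Hypertension, r = 3: 1.096/1.060 = 1.034.
- Diabetes, r = 1.5: 1.065/1.050 = 1.014.
- Medicaid, r = 1.3: 1.039/1.030 = 1.009.
- All three in the same direction, taken as independent: 1.034 × 1.014 × 1.009 = 1.058, rounded to 1.06.

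More generally, one binary factor at an ASD of exactly 0.1, with unexposed prevalence 2–50%, gives a bias of about 1.01–1.02 for r = 1.5, 1.02–1.04 for r = 2 and 1.03–1.06 for r = 3.

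**Step 3: rate of declared elevated risk when the true RR is 1.** Rate = P(Z > 1.96 − ln(bias)/SE), with SE = √{2[1/(15000p) − 1/15000]}, where p is the outcome incidence. Nominal rate: 2.5%.

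| Incidence | SE | Bias 1.034 | Bias 1.06 |
|---|---|---|---|
| 0.1% | 0.365 | 3.1% | 3.6% |
| 0.3% | 0.210 | 3.6% | 4.6% |
| 0.5% | 0.163 | 4.0% | 5.5% |
| 1% | 0.115 | 4.8% | 7.3% |
| 2% | 0.081 | 6.1% | 10.8% |
| 3% | 0.066 | 7.3% | 14.2% |

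**Step 4: bias in the other direction.** With a true RR of 1.2 at 3% incidence (same SE), detection is 79% without bias, 62% if the RR is divided by 1.034 and 47% if divided by 1.06.

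**Step 5: the same bias against a margin of 2.** At 1% incidence, true RR 1 and no other bias, non-inferiority power is Φ[ln(2/bias)/SE − 2.498], where SE = √[(1 − 0.01)/150 + (1 − 0.01·bias)/(150·bias)]. Without bias it is Φ(0.693/0.1149 − 2.498) = 99.98%. With bias 1.06 it is Φ(0.635/0.1132 − 2.498) = 99.91%. The same bias takes the secondary signal rate from 2.5% to 7.3%.

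**The case against.** **Which rule is weaker.** A reader might infer that the secondary endpoints get the weakest adjustment in the plan. The documents do not support that. A secondary model takes every covariate with ASD above 0.1, while a primary model discards those, outside the forced list, that fail the 10% filter. A secondary model may therefore hold more covariates than a primary one. This objection stands.

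**Size.** The loss arises only at an ASD of 0.1 or less, and the example puts several factors just under the cut-off in the same direction. The 3% row fits few endpoints. Robust variance, the plan's marker for incidence above 2%, is assigned outright only to poor fetal growth and conditionally to congenital anomalies, which are analysed by type. Transfusion is expected below 2% (rationale for protocol amendment 2). For rare endpoints the inflation is slight. This also stands.

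**General wording.** SAP 4.1 says "Potential confounders will be determined based on bivariate analyses and scientific relevance (see Section 3.2.4", and protocol 6.2.1 admits prior knowledge, either of which could bring the four factors in. But SAP 3.2.4 makes the numbered steps the working rule, and step 5 does not use that latitude.

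**Consequences.** Secondary analyses are for signal detection, SAP 5.2 accepts easier rejection of RR = 1, and SAP 4.5 investigates signals, with stratified incidence by risk factor (table shell 10 names diabetes). This lowers the stakes. However, SAP 5.2 argues from multiplicity, not confounding; stratified description is not a re-adjusted estimate; and a masked secondary signal triggers no investigation.

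**Larger biases remain.** The 1.25 design bias allowed for in SAP 3.3 would by itself give signal rates of about 49% at 1% incidence and 92% at 3%. Adjusting for four factors will not make these tests well calibrated. That is no reason to leave out measured prognostic factors already in hand.

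**Conclusion.** The gap is real and modest. Steps 4 and 5 treat the same prognostic factors differently without explanation, and the endpoints that lose the guarantee are those tested against RR = 1.

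Under the assumed prevalences and outcome RRs, the elevated-risk rate rises from 2.5% to 3.1–3.6% at 0.1% incidence, 4.8–7.3% at 1% and 7.3–14.2% at 3%. The lower figure is for one strong factor, the upper for three aligned ones. A several-fold rise is confined to the commoner outcomes, mainly poor fetal growth.

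A reader might also conclude that the plan will produce false signals. That goes too far: the effect requires a forced factor to be imbalanced below the cut-off and clearly prognostic, and the bias may run downward and hide a signal instead. None of this affects the stated primary power.

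**What to change.** Amend step 5 so that the adjusted model for each secondary endpoint contains the four step 4 factors plus all covariates with ASD above 0.1, where event counts allow. State in advance what event count is required; below it, step 5 applies as now written. Keep the existing non-convergence and fewer-than-5-events rules. Do not remove covariates with ASD above 0.1 in order to retain forced factors that turn out balanced, since that could worsen confounding for sparse endpoints. If the different rule is intended, give the reason and reconcile step 5 with the scientific-relevance wording of SAP 4.1 and with protocol 6.2.1.

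The cost is small. The covariates are already collected. The four factors need about six parameters: one each for diabetes, hypertension and Medicaid, one for hospitalization or ED visit, and two for the three-level outpatient count. Fewer are added where some already exceed the cut-off. Intervals for the less common endpoints become slightly wider. Settling this before analysis also avoids choosing the adjustment after a signal has been seen.
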